6.2 Methods of minimising bias

6.2.1 Randomisation

We will use a centralized computed randomization process to randomize participants into the intervention and control arm at a 1:1 ratio. The central server will be located in a protected environment at CTU Bern.

6.2.2 Blinding procedures

Participants, nurses and investigators will not be blinded. We will blind both the statisticians who perform the main analyses and the laboratory personnel who determine urinary cotinine, anabasine, VOCs, TSNA (NNN, NNK and its metabolite NNAL) and PAHs (1- and 2-Naphtol and 1-OHP) levels.

6.2.3 Other methods of minimising bias

To minimize bias of safety outcomes, all clinical events (hospitalizations) and other serious adverse events will be verified by a blinded external committee whenever possible (see 1.7.3).

6.3 Unblinding Procedures (Code break)

Not applicable.

7. STUDY POPULATION

7.1 Eligibility criteria

Subjects fulfilling all of the following inclusion criteria are eligible for the study:

- Informed Consent as documented by signature
- Persons aged 18 or older
- Currently smoking 5 or more cigarettes a day, for a least 12 months
- Willing to try to quit smoking within the next 3 months
- Persons providing a valid phone number, a valid email address and/or a valid postal address.

The presence of any one of the following exclusion criteria will lead to exclusion of the subject:

- Known hypersensitivity or allergy to contents of the e-liquid
- Participation in another study with investigational drug within the 30 days preceding the baseline visit and during the present study where interactions are to be expected
- Women who are pregnant or breast feeding
- Intention to become pregnant during the course of the scheduled study intervention, i.e. during the first 6 months of the intervention
- Persons having used ENDS or tobacco heating systems regularly in the 3 months preceding the baseline visit
- Persons having used nicotine replacement therapy (NRT) or other medications with demonstrated efficacy as an aid for smoking cessation such as varenicline or bupropion within the 3 months preceding the baseline visit
- Persons who cannot attend the 6-month follow-up visit for any reason
- Persons who cannot understand instructions delivered in person or by phone, or otherwise unable to participate in study procedures

7.2 Recruitment and screening

Target population of the study are individuals who smoke 5 or more cigarettes/day since more than one year and are willing to try and quit within the next three months. Individuals will be recruited through media advertisements and communications. Interested smokers will be screened over the phone by a trained nurse to review eligibility criteria. Smokers will also announce their target quit date and, if eligible and if they have no contra-indications for participating in the study, will be sent a participant information sheet and the informed consent form. The baseline visit will be scheduled a week before the quit date they named over the phone. At the baseline visit, trained study nurses will again verify the eligibility criteria, explain the trial and have participants sign the informed consent form.

7.3 Assignment to study groups

We will randomize participants to either intervention or control group at the end of the baseline visit, after participants have signed the consent form and we have taken all baseline measures. Nurses will collect all demographic parameters from participants online before they can request centralized randomization. Once all parameters are entered, the nurse will request a randomization allocation in presence of the participant. The central server located in a protected environment at CTU Bern will then allocate participants in the intervention and control group in a 1:1 ratio. Nurses and participants will learn about the allocation group directly on the screen, hence the nurse and participants will not be blinded. The randomization lists stored on the server will be only accessible by system administrators and not to study personnel involved in the recruitment of participants. The centralization of process and necessity to enter all demographic data before being able to randomize participants in the intervention and control group will ensure the reliability and concealment of the randomization process.

7.4 Criteria for withdrawal / discontinuation of participants

Discontinuation of treatment

Treatment will be discontinued if:

- A participant reports she is pregnant.

Treatment may be discontinued if:

- Participants do not comply with the instructions by the research team;
- A treatment-related SAE is suspected;
- The protocol has been irretrievably violated, as determined by the sponsor.

Subjects who permanently discontinue study treatment are encouraged to continue in the follow-up period and to attend the protocol-specified follow-up visit at 6-, 12- and 24- month follow-up visits in accordance with the intention-to-treat principle.

Discontinuation of participation in the study

Participation in the trial will be stopped if:

- participants make a request to discontinue their participation

Participation in the trial may be stopped if:

- the responsible study investigator decides that continued participation in the study could be harmful to the subject's wellbeing

A participant who decides to discontinue the study participation prematurely will be defined as a dropout if he/she has already been randomized. A study participant who terminates the study before being randomized will be defined as a screening failure.

Participants who cannot be reached over the phone at follow-up visits will not be excluded. Participants who do not present at the 6/12/24-month visits will be contacted by phone, by letter, and, finally, we will contact two contact persons and the primary care provider listed by participants at the baseline visit. If we cannot contact participants for more than three months, we will consider them lost to follow-up.

Participants who have finished their study at 6 months according to their signed informed consent will be contacted by phone or by e-mail to ask if they would like to continue their study participation for the 12- and 24-months visit. If they don't wish to continue or if they are unreachable no further contact attempts will be performed. These participants will be considered as having finished the study according to the protocol.

8. STUDY INTERVENTION

8.1 Identity of Investigational Products (treatment / medical device)

8.1.1 Experimental Intervention (treatment / device)

Device:

We will use the Innokin Endura T20-S starter kit. The Endura T20-S kit will come in a user packet with a 1,500 mAh internal Li-Po battery, a Prism S Coil (0.8 ohm) atomizer, a spare drip tip, a micro USB DC 5V/1A cable and an instruction manual in French or German, respectively. Colors available will be Black, Purple, Grey, Red and Blue.

<https://www.innokin.com/vaporizers/endura-t20-s/>

E-liquids:

We use the e-liquids produced by the company Gaiatrend in France (<https://www.gaiatrend.fr/en/>). Nicotine concentrations available will be 0 mg/ml, 6 mg/ml, 11 mg/ml and 19.6 mg/ml. Following aromas will be available to be chosen by the study participants: FR-4 (tobacco flavor) and FR-M (tobacco flavor), FRESH MINT (menthol flavor), RASPBERRY#2 (fruity flavor), RED FRUITS (fruity flavor) or GREEN APPLE (fruity flavor). The proportion of propylene glycol and vegetal glycerin will be 76/24 for all e-liquids. The components of the e-liquids will be propylene glycol, vegetal glycerin, medical-quality nicotine, alcohol and aromas.

<https://www.gaiatrend.fr/en/>

Study participants in the intervention group will be advised by trained study nurses how to get started with the device, how to fill the device with e-liquid, how to charge the device and how to change the coil every two weeks. A user manual will be provided for every study participant.

Participants will be advised to only use liquids we provide. To avoid odor disturbances, e-liquids should be stored in a food storage plastic or glass box. The box should to be sealed and not stored with food. After use, the box cannot be used for storing food. The box should be stored out of reach of children as normally done with cleaning products and detergents.

<http://www.innokin.com/manuals/Endura-T20S.pdf>

8.1.2 Control Intervention (standard/routine/comparator treatment / medical device)

Participants in the control intervention will receive SOC only. SOC is as follows: Study nurses will provide SCC based on cognitive behavior therapy and motivational interviewing (see e.g., ¹⁵⁰). Trained nurses will follow a standardized course. SCC will be provided by person at the first clinical visit (baseline visit) and then over the phone at the target quit date, at week 1, 2, 4, and 8. Then again at the 6-, 12- and 24-months follow-up visits. Average duration of counseling is expected to be 15 minutes over the phone and at the follow-up visits and 30 minutes during the baseline in-person visit. Participants will be allowed to use other NRT, smoking cessation medication or smoking cessation help at their own expenses. Participants interested in other evidence-based smoking cessation drug therapy (varenicline or bupropion) will be allowed to consult their primary care physician (PCP) or another health professional to get a prescription for these drugs. They will also be encouraged to go on the stop-tabac.ch (www.stop-tabac.ch) website for smoking cessation support if they wish online support, as is currently performed in smoking cessation counseling in Switzerland.

8.1.3 Packaging, Labelling and Supply (re-supply)

Device:

The Endura T20-S kits will come in a user packet with a 1,500mAh internal Li-Po battery, a Prism S Coil (0.8 ohm) atomizer, a spare drip tip, a micro Micro USB DC 5V/1A cable, a USB charger and an instruction manual. Colors available will be Black, Purple, and Blue (see image of the kit below and also images of the device in section 8.1.1.).

The kits will be ordered at Innokin and stored in each center. They will be handled directly in person by the study nurse at the first visit for the intervention group at no charge. Participants will receive two devices at the baseline visit. In case of defective devices which need to be replaced, or if the device is lost or otherwise unusable, participants will either directly visit the centers to pick up replacement devices, or participants will get the possibility to re-order a device through the study nurse at any time during the first 6-months follow-up by mail. In all cases the devices will be free of charge for participants during the 6-months follow-up. If participants are interested in getting a new device provided by the study after the 6-months follow-up visit, they will have to purchase them at their own cost wherever available. Free E-cigarettes and coils will not be provided anymore by the study personnel after the 6-months visit.

E-liquids:

All e-liquid bottles will follow standards by the EU and be limited to 10 ml. They will include a safety notice and logos to indicate that the product is toxic, that bottles should not be used by minors under 18 and not to be used by pregnant women. The bottle will contain information on the composition, the nicotine concentration, the flavour and have a warning reading: "This product contains nicotine, which is a highly addictive substance". Gaïatrend obtained ISO8317 certification for its e-liquid flasks (See also section 8.1.1. for pictures of the flasks containing the e-liquids). This standard certifies that flasks are equipped with child-resistant closures (See Section 3.7 Risk/benefit).

At the baseline visit, study participants will be allowed to taste and choose between six e-liquid flavors and between four different nicotine concentrations. Once they have tested and chosen their e-liquid, they will directly receive a first batch of e-liquids.

At regular phone intervals from study nurses to study participants participants will be allowed to switch between flavor and nicotine concentration during the course of the study. Study nurses will support participants in the progressive reduction in nicotine concentrations over time to avoid withdrawal symptoms, in particular the management of the liquid concentrations used. In addition, if participants use all the e-liquid during follow-up, and given that the use of e-liquids will be *ad libitum*, participants will be allowed to reorder e-liquids through contacting the study nurses during the first 6 months. For those still interested to use e-liquids after the first 6 months, they will have to purchase them wherever available at their own cost. Free e-liquids will not be provided anymore by the study personnel after the 6-months visit.

Batches of e-liquids will be shipped and mailed by Gaïatrend to the study centers.

8.1.4 Storage Conditions

Batches of e-liquids will be shipped and mailed by Gaïatrend to the study centers. The devices and e-liquids will be stored in each center at room temperature in a securely locked cabinet or enclosure. Access will be limited to investigators and their designees.

Participants will be instructed to store the e-liquids in a dry place, at room temperature and out of reach of children and pets. After study termination, participants will be allowed to keep their devices and spare e-liquid or return them in each center if not completely used. To avoid odor disturbances, e-liquids should be stored in a food storage plastic or glass box. The box should be sealed and not stored with food. After use, the box cannot be used for storing food. The box should be stored out of reach of children as normally done with cleaning products or detergents.

In case of malfunction of the devices or identification of damage to the e-liquids bottles by participants during shipping, participants will be encouraged to call the study nurse, to return the devices or e-liquids and be sent new devices or e-liquids by mail.

8.2 Administration of experimental and control interventions

8.2.1 Experimental Intervention

After the randomization process, participants in the intervention group will receive a structured intervention for smoking cessation and in addition, two devices and e-liquids at no charge and advice on how to use them by trained study nurses. Participants will be explained the rationale behind delivering nicotine through the e-liquids instead of the cigarettes and be trained in using the device, for example how to turn in on and off, charge the device, refill the 2 ml tank with e-liquids and replace the coil at

regular intervals. Participants will be allowed to taste and choose between the various nicotine concentrations and flavors. We will encourage study participants to use the highest nicotine concentration in order to ensure optimal nicotine substitution while reducing the volume of e-liquids used and vapor inhaled. Study nurses will teach participants how to recognize withdrawal symptoms (craving, changes in mood etc.) and instruct them to use more liquid or a higher concentration if they experience withdrawal symptoms. Once they have decided of the nicotine concentration (either 0 mg/ml, 6 mg/ml, 11 mg/ml or 19.6 mg/ml) and the aroma (among two different tobacco flavors, menthol flavor or three different fruity flavors), they will receive a first batch of e-liquids directly at the baseline visit in preparation of their smoking cessation attempt scheduled one week later. Participants will be free to use their ENDS as much as they wish. They will be informed that they can switch nicotine concentrations and flavors at any time during follow-up. They will also be informed that they can re-order e-liquids as much as they want over the first 6 months of follow-up. We will document ENDS use by monitoring the use of e-liquids in ml.

After this first visit, study nurses will contact participants in both study groups over the phone on the day of the target quit date, then again after 1 week, 2 weeks, 4 weeks and 8 weeks. During these follow-up calls, study nurses will provide SSC and ask participants about their use of tobacco cigarettes and ENDS and answer technical questions, ask if participants need additional e-liquids or if they want to shift to another nicotine concentration or flavor. Study nurses will support participants in the progressive reduction in nicotine concentrations over time to avoid withdrawal symptoms, in particular the management of the liquid concentrations used. Study nurses will record the time spent on the phone with each participant. Nurses will also encourage participants the change of coil at regular intervals if they continue using ENDS. Between these scheduled visits, participants will have the possibility to contact study nurses anytime during office hours, send an email to study nurses for any technical issues with the device or smoking cessation support. Nurses will answer emails within 24 hours of receipt on office days.

Average duration of counseling is expected to be 15 minutes over the phone and during the in-person visits at 6-, 12- and 24- month follow-up visits and 30 minutes during the in-person visit at baseline. Participants will be allowed to use other NRT, smoking cessation medication or smoking cessation help at their own expenses. Participants interested in other evidence-based smoking cessation drug therapy (varenicline or bupropion) will be allowed to consult their primary care physician (PCP) or another health professional to get a prescription for these drugs. They will also be encouraged to go on the stop-tabac.ch (www.stop-tabac.ch) website for smoking cessation support if they wish online support, as is currently performed in smoking cessation counseling in Switzerland.

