8.2.2 Control Intervention

Participants in the control intervention will receive SOC only in person at the baseline visit and then over the phone.

After this first visit, study nurses will contact participants in both study groups over the phone on the day of the target quit date, then again after 1 week, 2 weeks, 4 weeks and 8 weeks. During these follow-up calls, study nurses will provide SSC and ask participants about their use of tobacco cigarettes. Study nurses will record the time spent on the phone with each participant.

Average duration of counseling is expected to be 15 minutes over the phone and during the in-person visits at 6-, 12- and 24- month follow-up visits and 30 minutes during the in-person visit at baseline. Participants will be allowed to use other NRT, smoking cessation medication or smoking cessation help at their own expenses. Participants interested in other evidence-based smoking cessation drug therapy (varenicline or bupropion) will be allowed to consult their primary care physician (PCP) or another health professional to get a prescription for these drugs. They will also be encouraged to go on the stop-tabac.ch (www.stop-tabac.ch) website for smoking cessation support if they wish online support, as is currently performed in smoking cessation counseling in Switzerland.

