9.2.4.1 Adverse events

For this trial, all AEs as well as all SAEs will be collected, fully investigated, and documented in the source documents and the eCRF for all participants from the date of ICF signature until the last protocol-specific procedure has been completed.

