6.6 Safety evaluation

Safety outcomes will be analysed using the ITT and PP set.

The safety analysis will list the number of patients dropping out for both treatment arms, including the reasons, and a list of events for patients dropping out, with the treatment group, relation, grade, type of AE and potential free text.

AEs and SAEs will be summarized by presenting for both treatment arms the number of any AE, any SAE, and the number and percentage of patients with any AE or any SAE.

Further, we will present the

- grade and relation of AEs and SAEs (number of patients with events and the number of events),
- category and grade of AEs and SAEs
- category and relation of AEs and SAEs
- AEs and SAEs stratified by consumption (cigarettes, ENDS, both, none)

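### From week 8 to month 6 the protocol describes between-visit nurse contact only for the ENDS arm, and the AE tables ignore how events came to light, so mild events could be recorded more often on ENDS

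*Supplement*

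**What the plan says.** **Scheduled contact is equal.** Protocol 8.2.1 and 8.2.2 both provide calls on the target quit date and "then again after 1 week, 2 weeks, 4 weeks and 8 weeks". For controls the text begins "After this first visit, study nurses will contact participants in both study groups over the phone on the day of the target quit date". The next scheduled contact is the month-6 visit. AE assessment is listed at each of these contacts for both arms (sections 9.1, 9.3.3 and 9.3.4).

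**Between-visit contact is described for one arm.**
- Section 8.2.1 adds: "Between these scheduled visits, participants will have the possibility to contact study nurses anytime during office hours". The sentence continues with e-mail, and covers both device problems and cessation support.
- Section 3.2 gives a direct nurse number under the training of intervention participants.
- Section 8.1.3 on e-liquid: "participants will be allowed to reorder e-liquids through contacting the study nurses during the first 6 months". On devices: "participants will get the possibility to re-order a device through the study nurse at any time during the first 6-months follow-up by mail".
- Section 8.2.2 repeats much of the call text, including "Study nurses will record the time spent on the phone with each participant", but leaves out the between-visit offer. It does not forbid contact.

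**AE collection and analysis.** Section 9.2.4.1 says "all AEs as well as all SAEs will be collected, fully investigated, and documented in the source documents and the eCRF for all participants", from consent to the last procedure. Protocol 11.4.5 compares AE proportions between groups. SAP 2.0, section 6.6 says "AEs and SAEs will be summarized by presenting for both treatment arms the number of any AE, any SAE", with the number and percentage of patients affected. It also stratifies by product consumed, but not by how an event was reported.

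**The concern.** An AE count depends on how often people are in touch with someone who can write the event down. From week 8 to month 6 an ENDS participant has described routes to the nurses and a supply reason to use them. A cough or sore throat mentioned on such a call may be entered at once. The same event in a control may have to survive in memory until month 6, which is 124 days (about 18 weeks) after the week-8 call.

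AEs are among the core secondary outcomes in SAP 6.1, and protocol 3.2 hypothesises that using ENDS in place of cigarettes will not increase them. Differential detection would work against that hypothesis, and a reader of the tables in 6.6 could not separate it from a real effect. The consumption strata would not resolve it, because those still using ENDS are the ones with reason to call. The blinded committee (SAP 2.8) checks events already recorded; it cannot recover unreported ones.

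**Working it through.** The documents give no AE rate, recall rate or unscheduled-contact rate, so there is no stated figure to reproduce. The timing and arm size come from the documents; the rest is assumed.

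**1. Length of the gap.** Week 8 is day 56 and month 6 is day 180 (protocol 9.1). Gap = 180 − 56 = 124 days; 124/180 = 69%. At the window limits: (152 − 63)/152 = 59% and (264 − 49)/264 = 81%.

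**2. Events in the gap, no true difference, 586 per arm.** Let p be the true share of participants with an AE in the gap, r the share of these captured at the common month-6 enquiry, and c the share of ENDS participants with an extra contact that captures the rest.

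- Recorded, control: p·r
- Recorded, ENDS: p·[r + c(1 − r)]
- Risk ratio: 1 + c(1 − r)/r, which does not depend on p

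Take p = 40% (assumed) and c = 30% (assumed; it equals the ENDS use that protocol 11.2 expects at month 6). The last column is the chance that a two-sided 5% test declares an ENDS excess (nominal 2.5% in that direction).

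| r | Control | ENDS | Risk ratio | False ENDS excess |
|---|---|---|---|---|
| 95% | 38.0% | 38.6% | 1.016 | 4.0% |
| 80% | 32.0% | 34.4% | 1.075 | 13.8% |
| 60% | 24.0% | 28.8% | 1.20 | 46% |

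At r = 100% the ratio is exactly 1. Over p = 20–60%, r = 40–95% and c = 10–60%, the ratio runs from 1.005 to 1.90 and the false-excess probability from about 3% to nearly 100%.

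**3. Whole six months, Poisson counts.** Let λ be the true mean number of AEs per person in both arms, with 0.689 of events in the gap (constant rate), and let c now be the share of otherwise forgotten events that is captured.

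- Control mean: λ[0.311 + 0.689r]
- ENDS mean: λ[0.311 + 0.689(r + (1 − r)c)]
- Share with any AE: 1 − exp(−mean)

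Results:
- λ = 0.5, r = 0.9, c = 0.2: rate ratio 1.015; difference in any AE 0.4 points.
- λ = 1.0, r = 0.8, c = 0.1: means 0.862 and 0.876; rate ratio 1.016; difference 0.6 points; false excess about 4%.
- λ = 1.0, r = 0.5, c = 0.4: means 0.656 and 0.793; rate ratio 1.21; 48.1% against 54.8%, a difference of 6.7 points; false excess about 63%.

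The sign is the same throughout. The size is governed by r and c, which the documents do not supply. If ENDS irritation occurs mostly early, less than 69% of events fall in the gap and the effect shrinks.

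**The case against.** A reader might infer that only the ENDS arm has nurse contact after week 8, that its participants must call whenever liquid runs out, and that every event mentioned on such a call must be recorded. The documents do not support these readings.

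- Control contact is not described, but it is not barred. The change history appended to the protocol records a 2019 letter to all participants, who were told to go on reporting adverse events to the nurses.
- The ENDS contacts are optional and started by the participant. The schedule in 9.1 places e-liquid orders at weeks 1, 2, 4, 8 and month 6, and nurses ask about supply during the scheduled calls. No passage makes a reorder an AE enquiry.
- Section 9.2.4.1 sets the scope of collection. Section 9.2.4 sets the method: proactive questioning at calls and visits with standardized questionnaires. That an event raised on a supply call is recorded is the natural reading of the scope, but remains an inference.
- At month 6 both arms get a structured AE assessment and questions on medication and recent antibiotics. The change history also reports systematic queries to hospitals and attending physicians for AEs.

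These points stand and narrow the problem to mild, self-limited events forgotten by month 6 or lost through non-attendance. They do not remove it, because none recovers a forgotten event that generated no care.

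A further objection concerns the remedy. Making scheduled-contact AEs the main comparison could drop real ENDS events already logged between visits and not repeated at month 6. That is right, and such a table should not replace the all-AE comparison.

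**Conclusion.** The point holds in limited form. For 124 of the 180 days neither arm has a scheduled contact, between-visit routes to the nurses are described only for ENDS participants, AE collection is open-ended, and the analysis does not distinguish how events came to light. Low-grade AE counts and the percentage with any AE could therefore lean towards an ENDS excess without a true difference.

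This rests on two assumptions: that AEs raised at unscheduled contacts are recorded, and that month-6 recall is incomplete. The bias is near zero if recall is near complete and larger if recall is poor. The 63% figure is one corner of an assumed grid and should not be read as a prediction; the plan does not establish that a false excess will occur. SAEs should be less affected, since hospital stays are better remembered and can be confirmed.

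**What to change.** **Protocol 8.2.2:** give controls the same between-visit contact offer as 8.2.1.

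**Month-6 AE enquiry (9.3.4):** ask both arms about the whole interval since the week-8 call, including events already reported, so that ENDS events logged earlier also appear at the common contact. Count each event once in the all-AE table.

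**SAP 6.6:**
- State how AEs raised at unscheduled contacts are recorded.
- Keep the all-AE comparison as the main table.
- Flag each AE as first reported at a scheduled or an unscheduled contact. The documents show no report-date field: the audit trail in 12.2.2 stamps data entry, which under 12.1.1 may follow a contact by two weeks. If the report date is not captured, add a field.
- Add a by-arm sensitivity table of AEs reported at the contacts common to both arms (day 0, weeks 1, 2, 4 and 8, month 6), and list unscheduled reports by arm.
- Keep all SAEs, from any source, in the SAE comparison.

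**Cost:** one flag (perhaps one eCRF field), one extra table, and some additional nurse time for controls. If data collection is already complete, only the SAP items remain possible. The sensitivity table would then need a caveat that ENDS events logged between visits may be missing from it.
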